7.6.2 Clinical Laboratory Evaluation

All descriptive summaries of laboratory results will be based on data analyzed by the local laboratory and presented in Système International (SI) units. All clinical laboratory data (hematology, serum chemistry, coagulation, urinalysis, and pregnancy test) will be listed. Laboratory measurements identified as abnormal (i.e., outside the normal range) will be flagged in the listings.

Clinical laboratory measurements, including hematology, serum chemistry, and coagulation, will be summarized by treatment group and overall. Descriptive statistics will be presented for observed values and changes from baseline at each visit where parameters were scheduled to be collected per the clinical study protocol.

Urinalysis parameters will be summarized using the following categories: normal, abnormal, not clinically significant or abnormal, clinically significant. A 3-by-3 contingency table will be presented to summarize the shift from the baseline category to the worst post-baseline category. Summary results will include the count and percentage of participants within each shift category and treatment group.

Where applicable, hematology, chemistry, and coagulation results for select parameters will be assigned a toxicity grade based on the NCI CTCAE, version 5.0. If the quantitative criteria for grading are equivalent for 2 grades and the differentiation is described by clinical interventions, the clinical intervention component will not be considered and the highest CTCAE grade will be assigned. Similarly, death related to AE (i.e., Grade 5) cannot be determined with available laboratory-based data collection and, thus, will not be summarized as a category. Laboratory parameters that include multiple sets of criteria for each direction (e.g., separate criteria for potassium measures to assess hyperkalemia and hypokalemia) will be summarized separately to reflect each set of criteria.

Syros Pharmaceuticals, Inc. SY-1425-301

Six-by-Six contingency tables will be presented for laboratory tests where toxicity grading can be applied to summarize the shift from the baseline grade to the worst postbaseline grade. Grades will be presented as none (Grade 0; i.e., measurements did not meet any CTCAE criteria for Grades 1 through 4), Grade 1, Grade 2, Grade 3, Grade 4, or missing grade. Summary results will include the count and percentage of participants within each shift category.

In addition, non-CTCAE-graded hematology, chemistry, and coagulation parameters will be summarized using the following categories: low, normal, high, and missing. A 4-by-4 contingency table will be presented to summarize the shift from the baseline category to the worst post-baseline category. Summary results will include the count and percentage of participants within each shift category and treatment group.

Prothrombin Time will not be summarized and will only be available in a listing. International Normalized Ratio (INR) will be summarized.

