1.3 Schedule of Activities

	Pre- screening (a) Day -45 to C1D1	Screening (a) Day -30 to C1D1		•				End of Treatment (EoT) (c)	Safety Follow- up (d) 30d post EoT (±3d)	Disease Follow- up (e) q3mo post EoT (±14d)	Survival Follow- up (f) q3mo post EoT (±14d)		
Study Day			D1 (g)	D2-7 (±2d)	D8 (±1d)	D22 (±1d)	D1 (±3d)	D2-7 (±2d)	D15 (±2d) (h)				
Pre-screening Informed Consent	X												
Main Informed Consent		X											
Eligibility Review (i)		X	X (i)										
Eligibility Approval Form (i)		X	X (i)										
Randomization (j)			X										
Medical History (k)		X	X										
Demographics		X											
ECOG Status		X	X				X			X	X		
Height		X											
Weight		X	X		X	X	X			X	X		
Vital Signs (l)		X	X	X (1)	X	X	X	X (1)	X	X	X		
Physical Examination (m) (n)		X	X		X (n)	X (n)	X (n)			X	X	X (n)	
Hematology (o), (p), (q)		X (p)	X		X	X	X (q)			X	X	X	

	Pre- screening (a) Day -45 to C1D1	Screening (a) Day -30 to C1D1			cle 1 Days		Cycles 2+ 28 Days Each (b)			End of Treatment (EoT) (c)	Safety Follow- up (d) 30d post EoT (±3d)	Disease Follow- up (e) q3mo post EoT (±14d)	Survival Follow- up (f) q3mo post EoT (±14d)
Study Day			D1 (g)	D2-7 (±2d)	D8 (±1d)	D22 (±1d)	D1 (±3d)	D2-7 (±2d)	D15 (±2d) (h)				
Serum Chemistries (o)		X	X		X	X	X			X	X		
Coagulation (o)		X	X				X			X	X		
Triglycerides, Total Cholesterol (o)		X	X				X			X	X		
Hepatitis Panel (r)		X											
Urinalysis (o)		X	X				X			X	X		
Pregnancy Test (s)		X	X				X			X	X		
Triplicate ECG (t)		X			X	X			X				
AE Monitoring (u)			X	X	X	X	X	X	X	X	X		
Prior/Concomitant Medication Review (v)		X	X	X	X	X	X	X	X	X	X		
RBC and Platelet Transfusions Recorded (w)		X	X	X	X	X	X	X	X	X	X	X	
Dosing Compliance/Diary Review					X	X	X		X	X			
HRQOL (EORTC QLQ-C30, EQ-5D-5L)		X	X				X			X	X	X	
Subsequent Anticancer Therapies (x)											X	X	X

CONFIDENTIAL

	Prescreening (a) Day -45 to C1D1	Screening (a) Day -30 to C1D1							End of Treatment (EoT) (c)	Safety Follow- up (d) 30d post EoT (±3d)	Disease Follow- up (e) q3mo post EoT (±14d)	Survival Follow- up (f) q3mo post EoT (±14d)	
Study Day			D1 (g)	D2-7 (±2d)	D8 (±1d)	D22 (±1d)	D1 (±3d)	D2-7 (±2d)	D15 (±2d) (h)				
Response Assessment (q), (y)							X (q), (y)			X (y)		X (y)	
Bone Marrow Aspirate		X (z)					X (aa)			X (aa)		X (bb)	
Transformation into AML							X			X		X	X
Overall Survival													X
Tamibarotene or Placebo (cc)					Dosii	ng D8-2	28 of ea	ich Cyc	le (cc)				
Azacitidine (dd)			X	X (dd)			X	X (dd)					

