An End of Treatment (EoT) Visit should occur within 3 days of the last dose of study drug (or within 3 days of decision to permanently stop drug treatment, if this decision directly follows a period when study drug has been on hold) and before the start of any subsequent anticancer therapy. A Safety Follow-up Visit should occur 30 days (±3 days) after the EoT Visit and if possible before the start of any subsequent anticancer therapy. After the EoT Visit, participants who have not progressed/relapsed will enter the Disease Follow-up period, during which response assessments will be performed for up to 5 years after discontinuation of study drug (irrespective of initiation of HSCT or other subsequent anticancer therapy) or until disease progression/relapse, death, or the occurrence of the expected number of OS events to support the final OS analysis, whichever occurs first. It is estimated that a final analysis of OS will occur approximately 70 months following the enrollment of the first participant.

Participants who progress/relapse will enter Survival Follow-up and will be followed to document the start of subsequent anticancer therapy, the date of transformation to AML, the date of death, and OS status until the expected number of OS events to support the final OS analysis is observed.

An Independent Data Monitoring Committee (IDMC) will be established and will review the data at the 2 planned interim futility analyses and the safety interims, as specified in the IDMC Charter.

Figure 1 Study Design

Abbreviations: MDS = myelodysplastic syndrome; RARA = retinoic acid receptor alpha

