6.4 Efficacy and Safety Endpoints

Unless otherwise specified, all efficacy and safety endpoints will use participants' all available data up to the data cut-off.

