6.4.2 Safety Endpoints

The safety endpoints for this study are incidence of adverse events (AEs) and changes in clinical laboratory values, electrocardiogram (ECGs), vital sign, and Eastern Cooperative Oncology Group (ECOG) measurements.

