7.6.1 Adverse Events

Treatment-emergent adverse events (TEAEs) are defined as those AEs with onset after the first dose of study drug or existing events that worsened after the first dose during the study up until the last dose of study drug + 30 days. TEAEs will be summarized by treatment group. Selected TEAEs will also be summarized. The selected TEAEs include rash, pain, hypertriglyceridemia, venous thrombosis, anemia/RBC count decreased, thrombocytopenia/platelet count decreased, neutropenia/neutrophil count decreased, and leukopenia/white blood cell (WBC) count decreased. A detailed search strategy for the selected TEAE groups is provided in Appendix 1.

AEs with missing start and/or stop dates will be considered TEAEs. Imputation rules for partial and missing dates are described in Table 10.

Verbatim terms on CRFs will be mapped to PTs and SOCs using MedDRA, version 23.1 or higher. AEs will be graded using the National Cancer Institute (NCI) CTCAE version 5. If an AE grade is missing, the previous worst grade under the same PT will be assigned if it is available, otherwise a grade of 4 will be assigned for classification purposes in the TLFs.

The CTCAE Grade will be summarized by grouping Grade 1 and Grade 2 together, then Grade 3 and Grade 4 together, as well as Any Grade for all relevant TEAE tables.

Summaries of the following types will be presented by treatment group:

• Overall summary of the number of TEAEs, TEAEs by relationship to tamibarotene/placebo and azacitidine, TEAEs by CTCAE grade, serious AEs (SAEs), SAEs related to tamibarotene/placebo and azacitidine, selected TEAEs, TEAEs requiring concomitant medications, TEAEs leading to dose interruption of tamibarotene/placebo and azacitidine, TEAEs leading to dose reduction of tamibarotene/placebo and azacitidine, TEAEs leading to discontinuation of
tamibarotene/placebo and azacitidine, TEAEs leading to death (overall summary will also be analyzed based on mITT who received at least 1 study dose)

- TEAEs by SOC and PT
- TEAEs by PT
- TEAEs occurring in $\geq 10\%$ of participants in any treatment group by PT
- TEAEs related to tamibarotene/placebo by PT
- TEAEs related to azacitidine by PT
- TEAEs by CTCAE grade, SOC and PT
- TEAEs by CTCAE grade and PT
- TEAEs related to tamibarotene/placebo by CTCAE grade and PT
- TEAEs related to azacitidine by CTCAE grade and PT
- SAEs by SOC and PT
- SAEs by PT
- SAEs occurring in \geq 5% of participants in any treatment group by PT

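### The hematology shift tables have no end date, so cytopenias arising after study drug has stopped, including after transplant, can set the worst grade

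*SAP*

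**What the plan says.** SAP 6.4.2 names "changes in clinical laboratory values" among the safety endpoints. SAP 6.4 sets the general rule that, unless another rule is given, "all efficacy and safety endpoints will use participants' all available data up to the data cut-off".

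In SAP 7.6.2, "hematology, chemistry, and coagulation results for select parameters will be assigned a toxicity grade" under CTCAE version 5, and contingency tables "summarize the shift from the baseline grade to the worst postbaseline grade". No closing date is given there, in SAP 7.6, in the missing-value rules of SAP 7.1.3.9, or in Protocol 9.4.4. SAP 7.1.2 keeps unscheduled values out of by-visit summaries but admits them when a worst post-baseline value is derived.

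In Protocol 1.3, the row beginning "Hematology (o), (p), (q" is marked at the Disease Follow-up visits, which take place every 3 months in patients who have not progressed or relapsed. SAP 6.1 says that response assessments in that period continue "for up to 5 years after discontinuation of study drug (irrespective of initiation of HSCT or other subsequent anticancer therapy"), unless progression, relapse, death or the final OS event count comes first.

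For adverse events, SAP 7.6.1 closes the treatment-emergent window: it runs "up until the last dose of study drug + 30 days".

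**The concern.** Cytopenia is a toxicity of azacitidine and a feature of the disease. Protocol 2.3 states that the combination showed no sign of additive hematologic toxicity over azacitidine alone, and a randomized comparison of worst hematology grades is a natural check on that statement. A nadir after a transplant or during a later regimen tells the reader nothing about it, yet under the plan it can be the single value that represents the patient.

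Two further problems follow. The laboratory tables and the adverse event tables would cover different periods for the same cytopenias: anemia, thrombocytopenia, neutropenia and leukopenia are all selected treatment-emergent events in SAP 7.6.1. And a worst-ever grade can only stay the same or worsen as draws accumulate, so it depends on how long each patient is observed off drug, which is not fixed by randomization.

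**Working it through.** The plan gives no figure to reproduce here. The check is a reading of the windows, plus arithmetic on visit counts.

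**1. Which window applies.** Laboratory change is a safety endpoint (SAP 6.4.2), the default is all data to cut-off (SAP 6.4), and SAP 7.6.2 states no exception. The window is therefore open until cut-off. This comes from the default combined with the silence of 7.6.2, not from an explicit statement in 7.6.2.

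**2. Which laboratory data exist after treatment.** In Protocol 1.3 the chemistry, coagulation, lipid and urinalysis rows end at Safety Follow-up. Hematology continues into Disease Follow-up. Survival Follow-up has no laboratory tests. The problem is thus essentially confined to hematology.

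**3. How many scheduled draws.** Five years is 60 months, and 60 / 3 = 20 draws per patient at most. Final OS analysis is expected about 70 months after first enrollment, so a patient with 60 months off drug must have enrolled and stopped within about 70 − 60 = 10 months of study start, then remained free of progression and relapse. One year off drug gives 12 / 3 = 4 draws. Protocol 1.3 footnote (e) and Protocol 8.1.1 omit the 5-year limit. Without it the ceiling would be 70 / 3, or 23 draws, so the change is small, but the texts should be reconciled.

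**4. How other analyses are bounded.**

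| Item | End of window | Source |
|---|---|---|
| Treatment-emergent adverse events | 30 days after last dose | SAP 7.6.1 |
| Concomitant medications | 30 days after last dose | SAP 7.3.7 |
| Deaths | split at 30 days after last dose | SAP 7.6.1 |
| HRQOL model | 30-day Safety Follow-up Visit | SAP 7.4.5.8 |
| Repeat of clinically significant laboratory values | Safety Follow-up at the latest | Protocol 8.2.6 |
| Hematology worst-grade shift | none stated; data cut-off by default | SAP 7.6.2 with 6.4 |

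The earliest scheduled Disease Follow-up draw, taking 3 months as 90 days as the SAP does in its loss-to-follow-up rule, is 90 − 14 = 76 days after the EoT Visit. All scheduled Disease Follow-up draws therefore lie outside the adverse event window.

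**5. Whether follow-up can differ by arm.** Entry to Disease Follow-up requires no progression or relapse, and time in it ends at progression, relapse or death. Protocol 7.1 permits transplant after study drug, and its rate is compared between arms as an exploratory endpoint. These are post-randomization outcomes that treatment may affect, so the number and kind of off-drug draws can differ by arm.

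**The case against.** **No attribution.** A reader might infer that these off-drug cytopenias are being counted as study-drug toxicity. The shift table assigns no cause; it grades values and displays them by treatment group. That stands. What remains is that on-treatment and post-treatment cytopenia are mixed in one safety table.

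**No established direction.** A reader might also infer that the more effective arm will look worse, because only patients without progression or relapse are followed. The documents do not support this. Responders may stay on study drug until a stopping criterion is met, so longer remission may mainly lengthen on-treatment time. Protocol 7.1 stops study drug in patients without at least hematologic improvement after the Cycle 7 Day 1 assessment. Those who have not progressed also enter Disease Follow-up, and they may be more common in the less effective arm. More transplants in one arm would push the other way. After CR or PR, a 50% fall in granulocytes or platelets is itself relapse (Protocol Appendix 8), so long-staying responders are selected for maintained counts. The net effect could go either way.

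**No usable magnitude.** One could assume a chance per draw of a new worst grade and compound it over 20 draws. The documents give no such rate, draws within a patient are correlated, 20 is a ceiling, and a draw matters only if it is worse than the patient's on-treatment worst. Such a calculation would not be evidence.

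**Limited reach.** The table is descriptive. Cytopenia adverse events are reported separately by grade and relatedness within a closed window, hematology is also summarized by scheduled visit, and all values are listed. This stands and limits the harm, but none of it corrects the worst-grade table.

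**Conclusion.** The point holds for hematology. Read as written, SAP 6.4 and 7.6.2 let Disease Follow-up draws and unscheduled values, including those taken after transplant or during another regimen, set the worst CTCAE grade. The resulting tables mix periods, do not match the cytopenia adverse event tables, and rest on follow-up time that can differ by arm.

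The size is known only as exposure: up to 20 scheduled off-drug draws per patient under the 5-year limit. How often such a draw would change a patient's worst grade, and which arm that would favor, cannot be determined from the documents. The conclusion assumes that the programming follows the SAP 6.4 default literally; an unwritten on-treatment filter would remove the problem but should then be written down. The analyses of CR and OS are unaffected. The change should be made because it corrects a safety comparison at little cost.

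**What to change.** In SAP 7.6.2, stated as an exception to SAP 6.4, define the window for worst post-baseline laboratory values as first dose of study drug through 30 days after the last dose. Exclude values on or after the start of HSCT or new anticancer therapy if that comes earlier. The first limit matches the adverse event rule. The second is stricter than that rule, and the SAP should say so. It is needed because the Safety Follow-up Visit precedes new therapy only where possible.

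The text should also settle one detail. The EoT Visit may fall up to 3 days after the last dose and the Safety Follow-up Visit up to 33 days after that, so a Safety Follow-up draw can fall at day 36 (3 + 33), or later if EoT follows a dose hold. State whether that draw counts.

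Keep all later values in the listings, and consider a supplementary all-data shift table so that delayed or persistent cytopenia stays visible. Reconcile the 5-year limit on Disease Follow-up between Protocol 4.1 and SAP 6.1 on one side and Protocol 1.3 footnote (e) and 8.1.1 on the other.

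The cost is a few lines of SAP text and one date filter, best settled before unblinding. The small downside is that late cytopenia leaves the main table, which the supplementary table offsets.

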7.6.2.1 Liver Safety Assessment

The following potentially clinically significant (PCS) criteria in liver function tests for alkaline phosphatase (ALP), alanine transaminase (ALT), total bilirubin (TB), aspartate transaminase (AST), INR, and their combination are defined as follows. The participant's worst post baseline value (highest for all parameters and lowest for ALP, for combination of values where ALP <2 × ULN) will be used.

- ALT or AST >3× upper limit of normal (ULN)
- ALT or AST >5×ULN
- ALT or AST >8×ULN
- ALT or AST >10×ULN
- ALT or AST $>20 \times ULN$
- TB >2×ULN
- ALP > $1.5 \times ULN$
- INR >1.5
- ALT or AST >3×ULN and TB >2×ULN (*)
- ALT or AST >3×ULN and INR >1.5 (*)
- ALT or AST >3×ULN and ALP <2×ULN and TB >2×ULN (*)

(*) Combination of values measured within same day or within 1 day apart

The number and percentage of participants with PCS values in liver enzymes and TB will be presented by treatment group. A listing of participants who met the above PCS criteria will be provided.

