5.1 Inclusion Criteria

Patients are eligible to be included in the study only if all of the following criteria apply:

- 1. Patients must be at least 18 years old at the time of signing of an informed consent.
- 2. Patients must be RARA-positive based on the investigational assay (Section 8.6.1).
- 3. Patients must be newly diagnosed with HR-MDS as follows:
 Diagnosis of MDS according to the WHO classification (Arber 2016) and classified by the IPSS-R risk category as:
 - a. Very High (risk score >6),
 - b. High (risk score >4.5 to 6), OR
 - c. Intermediate (risk score \geq 3 to 4.5).
- 4. Patients must have measurable disease with bone marrow blasts >5% at the Screening Visit.
- 5. Patients must have ECOG Performance Status of <2.
- 6. Patients must have adequate organ function, as defined by:
 - a. total bilirubin $\leq 3.0 \times$ the ULN,
 - b. ALT and AST $\leq 3 \times$ ULN, and
 - c. creatinine clearance ≥30 mL/min based on the Cockcroft-Gault Glomerular Filtration Rate estimation.

- 7. Patients must have a serum/high-sensitivity urine pregnancy test (for females of childbearing potential) that is negative at the Screening Visit and immediately prior to initiation of treatment (first dose of study drug).
- 8. Patients must be willing and able to comply with the scheduled study visits, treatment plans, laboratory tests, use of 2 methods of birth control (including a barrier method) for WOCBP and male patients (as described in Appendix 4), and other procedures.
- 9. Patients must be capable of giving signed and dated IRB or IEC approved informed consent document.

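### The starred liver combinations carry two unreconciled rules (worst value per parameter, and values within 1 day) that, read literally, drop true concurrent cases; the bilirubin rows also take no account of baseline

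*SAP*

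**What the plan says.** SAP 7.6.2.1 (Liver Safety Assessment) lists single-parameter criteria for ALT/AST, TB, ALP and INR, and three combinations. Its opening covers the parameters and their combination alike, and fixes the value to be used: "The participant's worst post baseline value (highest for all parameters and lowest for ALP" in the combination where ALP is below 2×ULN).

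The three combinations are ALT or AST >3×ULN with INR >1.5; "ALT or AST >3×ULN and TB >2×ULN"; and "ALT or AST >3×ULN and ALP <2×ULN and TB >2×ULN". Each carries an asterisk whose note reads "Combination of values measured within same day or within 1 day apart".

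The output is a count: "The number and percentage of participants with PCS values in liver enzymes and TB will be presented by treatment group". A listing of the participants who met the criteria is also planned. No criterion refers to baseline.

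Protocol 5.1, criterion 6, sets the entry limits: "total bilirubin $\leq 3.0 \times$ the ULN" and "ALT and AST $\leq 3 \times$ ULN".

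**The concern.** Both rules apply to the same three rows. The worst-value rule reduces each participant to one number per parameter over the post-baseline period. The asterisk rule then asks whether those numbers were drawn within a day of each other. A participant can have a true concurrent combination on one day and a higher ALT, a higher bilirubin or a lower ALP on another. Taken literally, the rules do not count that participant. Two competent programmers could produce different tables from this text.

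These rows look for uncommon events, so one participant more or fewer can change how the table reads. The bilirubin threshold raises a second problem: it lies inside the range allowed at entry, so the TB-based rows can count a pre-existing elevation.

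**Working it through.** The plan states no figure for this table, so there is nothing to reproduce. The check is to apply the rules to constructed cases.

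**Three ways to code the starred rows**

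1. Literal: take the highest ALT/AST, highest TB (or INR) and lowest ALP after baseline; the thresholds must be met and those extremes must lie within 1 day of each other.
2. Extremes only: as above, but with the asterisk rule ignored.
3. Any set: count the participant if any post-baseline values within 1 day of each other meet all thresholds.

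**Simplest case.** Cycle 3 Day 1 is study day 2×28+1 = 57, and Cycle 6 Day 1 is day 5×28+1 = 141. Suppose ALT is 4×ULN with TB 2.5×ULN on day 57, and ALT is 6×ULN with normal TB on day 141. Day 57 meets the ALT/AST plus TB row (4 >3 and 2.5 >2). Under coding 1 the ALT used is from day 141 and the TB from day 57. They are 141−57 = 84 days apart, so the participant is not counted.

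**Further constructed cases** (values in ×ULN, invented for illustration). Results are in the order coding 1 / 2 / 3.

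| Case | ALT/AST + TB | ALT/AST + ALP + TB |
|---|---|---|
| A: day 57 ALT 4.0, TB 2.5, ALP 1.2; day 85 ALT 6.0, TB 1.0, ALP 0.8; day 113 ALT 1.0, TB 3.0, ALP 1.1 | no / yes / yes | no / yes / yes |
| B: day 57 ALT 4.0, TB 1.0; day 85 ALT 1.0, TB 2.5; ALP 1.0 throughout | no / yes / no | no / yes / no |
| C: day 57 ALT 4.0, TB 2.5, ALP 1.5; day 85 ALT 1.0, TB 1.0, ALP 0.8 | yes / yes / yes | no / yes / yes |
| D: as C, but ALP 3.0 on day 57 | yes / yes / yes | no / yes / no |
| E: TB 2.5 at entry and unchanged; ALT 0.8, ALP 1.0 | no / no / no | no / no / no |

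In A, the literal coding loses a true same-day event in both rows. In C, it loses the three-way event only because ALP was lower on a later day; ALP at the time of the event need not be the participant's minimum. B and D go wrong only under coding 2.

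**INR row.** In the Schedule of Activities (Protocol 1.3), serum chemistry is drawn on Cycle 1 Days 8 and 22 but coagulation is not. If a participant's highest ALT falls on either day, no scheduled INR lies within 1 day. The literal coding then also rejects a later visit where ALT and INR were both raised.

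**Baseline bilirubin.** Entry permits TB ≤3.0×ULN and the criterion is TB >2×ULN, so every eligible value above 2 and up to 3×ULN already exceeds it. Case E is counted in the TB row under every coding. If ALT then rises above 3×ULN while TB stays at 2.5×ULN, the ALT/AST plus TB thresholds are met on the ALT change alone. ALT and AST do not share this problem: entry is capped at 3×ULN and the criterion is above 3×ULN.

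**Size.** The documents give neither the frequency of these events nor the share entering with TB above 2×ULN. A simulation can show only that the loss under coding 1 need not be trivial. It assumed lognormal ALT and TB with median 0.6×ULN, log-scale subject SD 0.35, t(6) visit errors scaled 0.40 and 0.35, 8 or 14 draws, and within-visit correlation 0.3 to 0.8. With the t errors combined linearly, 3% to 25% of true concurrent ALT and TB cases were missed. With correlated normals scaled by independent chi-squares, the figure was about 12% to 28%. Every input is assumed, and AST, INR and ALP were not modelled.

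**The case against.** The best defence is that the asterisk note is the specific rule for these rows and speaks of measured values, not worst values. A sensible programmer could find concurrent values first and take the worst within that window. Nothing would then be missed, and ALP would come from the right day. That reading is possible, but the SAP does not state it. The worst-value sentence expressly reaches the combinations through its clause on lowest ALP.

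A reader might infer that the plan combines unrelated peaks, or uses a low ALP from months later to satisfy the three-way row. It does not prescribe this: the asterisk rule forbids it for all three combinations, and cases B and D are misclassified only if a programmer ignores that rule.

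A reader might also infer that raised entry bilirubin is reported as a new finding. The SAP never says new or treatment-emergent here; it counts participants with PCS values regardless of baseline. Absolute thresholds are a legitimate choice, and randomisation means that raised baseline bilirubin is not expected to favour either arm.

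Other safeguards exist. Investigators review every laboratory report and record clinically significant changes as adverse events (Protocol 8.2.6), the IDMC meets about every 4 months to review safety (Protocol 10.1.4.1), and all laboratory data are listed (SAP 7.6.2). These limit the harm but do not repair the table. The shift tables in SAP 7.6.2 show one parameter at a time and cannot show concurrence. A missed combination could be recovered only by manual review of the full laboratory listings.

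**Conclusion.** The concern holds as an unreconciled derivation rule that undercounts when read literally, together with TB-based rows that take no account of an entry limit above their own threshold. The first part rests on reading worst as worst over the whole post-baseline period, which the text supports but does not force. The second needs no interpretation; it follows from comparing the entry limit with the criterion.

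The reach is small. One descriptive safety table and its listing are affected; the CR and OS analyses and their error control are not. No expected number of miscounted participants can be derived from the documents, and the simulated ranges should not be taken as estimates for this trial. The change should still be made, because the rows concern uncommon events and the remedy is cheap.

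**What to change.** In SAP 7.6.2.1:

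- Restrict the worst-value rule to the single-parameter rows.
- For the starred rows, state that a participant is counted if any set of post-baseline values, scheduled or unscheduled, drawn within 1 day of each other meets all thresholds of the row. Take ALP from that same set, and delete the clause on lowest ALP.
- Build the PCS listing from the same derivation, and show the dates and values of the qualifying set.
- Present every row that uses TB separately for baseline TB ≤2×ULN and >2×ULN.

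The thresholds stay as they are. The cost is a few lines of SAP text and a small change to the derivation program, using data already collected.
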